GCP	Good Clinical Practice
hCG	Human Chorionic Gonadotropin
HR	Heart Rate
ICF	Informed Consent Form
ICH	International Conference on Harmonization
IND	Investigational New Drug
IOP	Intraocular Pressure
IP	Investigational Product
IRB	Institutional Review Board
ITT	Intent-to-Treat
IWRS	Interactive Web Response System
LASIK	Laser-Assisted In Situ Keratomileusis
LDPE	Low Density Polyethylene
LOCF	Last Observation Carried Forward
logMAR	Logarithm of the Minimum Angle of Resolution

mmHg	Millimeters of Mercury
MedDRA	Medical Dictionary for Regulatory Activities
MOPs	Manual of Procedures
OAG	Open-Angle Glaucoma
OHT	Ocular Hypertension
OTC	Over-the-Counter
OU	Both Eyes
PM	Evening
PP	Per Protocol
PRK	Photorefractive Keratectomy
PT	Preferred Term
QD	Once Daily
ROCK	Rho Kinase
Rx	Medical Prescription
SAE	Serious Adverse Event
SAR	Suspected Adverse Reaction
SAS	Statistical Analysis Software
SD	Standard Deviation
SITA	Swedish Interactive Thresholding Algorithm
SLT	Selective Laser Trabeculoplasty
SOC	System Organ Class
SOP	Standard Operating Procedure
SSAR	Serious Suspected Adverse Reaction
SUSAR	Serious Unexpected Suspected Adverse Reaction
UA	Urinalysis
US	United States
VFQ-25	National Eye Institute Visual Function Questionnaire-25

1. INTRODUCTION

1.1 Investigational Product

Glaucoma is a progressive optic neuropathy that causes characteristic loss of visual fields and can eventually lead to blindness. A major risk factor for glaucomatous visual field loss is elevated intraocular pressure (IOP) ([AGIS 2000](#)).

The need for improved efficacy of glaucoma medications is supported by several clinical studies. Studies such as the Early Manifest Glaucoma Trial ([Heijl 2002](#)), the Ocular Hypertension Treatment Study ([Kass 2002](#); [Kass 2010](#)), and the Collaborative Normal Tension Glaucoma Study Group ([Collaborative Normal-Tension Glaucoma Study Group 1998](#)) support the general conclusion that every millimeter of reduction in IOP is significant for delaying disease progression. This conclusion holds true not only for high risk ocular hypertensive and glaucoma subjects with elevated IOPs but also for glaucoma subjects with IOPs in the normal range. Thus, the goal for treating subjects should be to lower IOP to the point that it prevents further damage to the optic nerve and achieve this without sacrificing safety or convenience.

Inhibitors of Rho kinase (ROCK) have emerged as a new class of IOP-lowering agents ([Chen 2011](#); [Kopczynski 2014](#)). Netarsudil mesylate (AR-13324) is a novel Rho kinase and norepinephrine transporter inhibitor developed at Aerie Pharmaceuticals. for topical ophthalmic use for lowering IOP. In both rabbit and monkey studies, netarsudil produces large reductions in IOP with a longer duration of action than reported for previously characterized Rho kinase inhibitors. Netarsudil ophthalmic solution has been shown to provide significant IOP lowering when dosed once-daily (QD) in the evening (Clinical Study Reports [AR-13324-CS202](#), [AR-13324-CS301](#), [AR-13324-CS302](#), and [AR-13324-CS304](#)), and reduces IOP potentially through several mechanisms: increasing trabecular outflow (Clinical Study Report [AR-13324-CS102](#); [Wang 2015](#)), decreasing aqueous humor production (Clinical Study Report [AR-13324-CS102](#); [Wang 2015](#)), and reducing episcleral venous pressure (Clinical Study Report [AR-13324-CS102](#); [Kiel 2015](#)). Aerie filed a New Drug Application for once-daily netarsudil 0.02% on February 28, 2017 (NDA 208254 for Rhopressa[®]) which was approved by US FDA on December 18, 2017.

Cornea verticillata, a whorl-like pattern of deposits typically localized to the basal corneal epithelium ([Mantjarvi 1998](#); [Hollander 2004](#)) have been reported in Aerie's completed Phase 3 studies ([AR-13324-CS301](#), [AR-13324-CS302](#), [AR-13324-CS303](#), and [AR-13324-CS304](#)). A variety of cationic, amphiphilic drugs are known to induce cornea verticillata, which arise due to the accumulation of phospholipids within corneal epithelial cells through a process called phospholipidosis (PLD). Amiodarone, an antiarrhythmic agent, is the most common cause of cornea verticillata, followed by chloroquine, hydroxychloroquine, indomethacin, and phenothiazines ([Raizman 2017](#)). It is unusual for these deposits to result in reduction of visual acuity or ocular symptoms, and the deposits typically resolve with discontinuation of the drug ([Mantjarvi 1998](#)). Corneal changes due to amiodarone have been studied over a long period of time and are well characterized; it is of

note that no routine monitoring, or specific treatment, or precautions are recommended for amiodarone-induced cornea verticillata ([Ingram 1982](#), [Siddoway 2003](#)).

The corneal verticillata associated with the use of netarsudil were first detected between 2-13 weeks, dose dependent, observed in 16.7% (76/454) of netarsudil QD subjects and 25.3% (64/253) of netarsudil BID subjects. Aerie carried out an observational cohort study ([AR-13324-OBS01](#)) to follow up the cases of cornea verticillata and demonstrated that cornea verticillata did not have any clinically meaningful impact on visual function and appeared to resolve after dosing was discontinued.

As part of the development plan in Japan, a Phase 1 ocular and systemic safety study comparing netarsudil ophthalmic solution 0.02% and 0.04% to placebo after a single dose and daily QD dosing over a 7-day period ([AR-13324-CS104](#)) in patients of Japanese ethnicity was recently completed in the United States. The study results demonstrated that the netarsudil 0.02% and 0.04 % formulations were safe and generally well tolerated by the healthy volunteer subjects of Japanese ethnicity within the 2nd generation who participated in this study.

The present study is a Phase 2 study to assess the efficacy and safety of netarsudil ophthalmic solution (0.01%, 0.02% and 0.04%) compared to placebo over a 28-day period in subjects with open-angle glaucoma (OAG) or ocular hypertension (OHT) in Japan.

1.2 Findings from Non-Clinical and Clinical Studies

Non-Clinical

Proof of concept for netarsudil in lowering IOP was established in primary pharmacology studies in 2 species, rabbits and monkeys. Safety pharmacology (central nervous system, respiratory, and cardiovascular) of netarsudil was investigated in rats and dogs. Pharmacokinetics/biodistribution of netarsudil was assessed after systemic and ocular administration of netarsudil. Ocular toxicity was investigated in studies up to 6 months in rabbits and up to 9 months in monkeys. Repeated dose toxicity of systemically administered netarsudil was investigated in studies up to 28 days in rats and dogs. Reproductive toxicity was investigated in rats and rabbits. The non-clinical program for netarsudil also included a standard range of genotoxicity tests and a phototoxicity study.

Clinical

The clinical development of netarsudil ophthalmic solution includes pharmacokinetics, tolerability, and dose-response investigations. The assessment of the ocular and systemic safety of netarsudil ophthalmic solution 0.02% in three Phase 1 clinical studies (Clinical Study Reports [AR-13324-CS101](#), [AR-13324-CS102](#) and [AR-13324-CS104](#) have been completed. Results from a previous Phase 2 study (Clinical Study Report [AR-13324-CS201](#)) investigating a range of netarsudil concentrations (0.01%, 0.02%, and 0.04%) were used to select the appropriate concentrations of netarsudil ophthalmic solution to be tested in the present study (0.01%, 0.02% and 0.04%). Four Phase 3 clinical studies (Clinical Study

Reports [AR-13324-CS301](#), [AR-13324-CS302](#), [AR-13324-CS303](#), and [AR-13324-CS304](#)) evaluating the safety and efficacy of netarsudil ophthalmic solution 0.02% have been completed.

Detailed information on nonclinical and clinical studies completed with netarsudil ophthalmic solution is provided in the [Investigator's Brochure](#).

1.3 Risks and Benefits to Human Subjects

Rhopressa[®] (netarsudil ophthalmic solution) 0.02% was approved in the US on December 18, 2017. In the US Phase 3 studies, AR-13324-CS301, AR-13324-CS302, and AR-13324-CS304, netarsudil ophthalmic solution 0.02% QD demonstrated non-inferiority to timolol 0.5% BID in subjects with OAG or OHT, and it was safe and generally well tolerated. The most common ocular adverse reaction observed in controlled clinical studies with Rhopressa[®] dosed once daily was conjunctival hyperemia which was reported in 53% of patients. Other common (approximately 20%) ocular adverse reactions reported were: cornea verticillata, instillation site pain, and conjunctival hemorrhage. Instillation site erythema, corneal staining, blurred vision, increased lacrimation, erythema of eyelid, and reduced visual acuity were reported in 5-10% of patients ([Rhopressa[®] PI](#)). The reader should refer to the Investigator's Brochure for more detailed information on potential risks due to use of netarsudil ophthalmic solution.

The major potential benefit from exposure to netarsudil ophthalmic solution is reduction in IOP in subjects with OAG or OHT. A long-term benefit of reduced IOP could be slowing of disease progression and preservation of vision in subjects when measured over periods of months to years.

2. STUDY OBJECTIVES

2.1 Primary Objective(s)

In this Phase 2 study, the primary objectives are:

[figure not shown]
- The ocular hypotensive efficacy of netarsudil ophthalmic solutions relative to placebo over a 28-day period
- The ocular and systemic safety of netarsudil ophthalmic solutions relative to placebo over a 28-day period

2.2 Secondary Objective(s)

None.

3. INVESTIGATIONAL PLAN

Figure 1 Study Design

3.1 Overall Study Design and Plan

This will be a double-masked, randomized, multicenter, placebo-controlled, parallel-group efficacy and safety trial evaluating reduction of elevated IOP with netarsudil ophthalmic solution over a 28-day treatment period. The purpose of this study is to assess the efficacy and safety of netarsudil ophthalmic solution (0.01%, 0.02% and 0.04%) compared to placebo in subjects that are 20 years of age or older with OAG or OHT in Japan.

All investigational products will be dosed in both eyes (OU) QD in the evening (PM). Subjects eligible to be enrolled in this study will be those with a diagnosis of either OAG or OHT. Approximately 208 subjects will be enrolled. Subjects who agree to participate in this study and are enrolled in the study will attend a total of 6 study visits: Screening Visit, Qualification Visit #1, Qualification Visit #2/Day 1 (baseline), Week 1 (Day 8), Week 2 (Day 15), and Week 4 (Day 29).

Subjects will be required to washout of their pre-study ocular hypotensive medication for a prescribed period (i.e., 5 days to at least 6 weeks, depending on the medication) prior to attending Qualification Visit #1. Subjects eligible to be enrolled in this study must meet all inclusion criteria and none of the exclusion criteria at each of the Screening Visit and Qualification Visits #1 and #2. Subjects will receive a baseline eye examination including IOP measurements at the Screening Visit and Qualification Visits #1 and #2, and undergo additional testing at Qualification Visit #2 including VFQ-25, BCVA, and CS testing. If deemed eligible, the subject will be enrolled at Qualification Visit #2 and assigned to placebo or 1 of 3 investigational products in a 1:1:1:1 ratio according to a computer-generated randomization list. Randomization will take place using IWRS methodology and will stratify subjects by site.

Randomized subjects will dose the assigned investigational product in both eyes QD in the evening (between 20:00 and 22:00 hours) beginning on Day 1 and up to and including the evening prior to the final visit at Visit 6 (Week 4). Procedures conducted at each of study Visits 4-6 will include safety measures and efficacy measurements, including IOP assessments. At Visits 4-6 (Weeks 1, 2, and 4, respectively), IOP will be assessed at 09:00, 11:00 and 16:00 hours. Following completion of the Visit 6 (Week 4) study visit procedures, subjects will exit the study. For subjects who discontinue early, every possible effort will be made to assure there is a final visit that includes all examinations listed for Visit 6.0 (Week 4) and dilated ophthalmoscopy.

For subjects who show any evidence of cornea verticillata by slit lamp examination using the grading system for amiodarone keratopathy (Orlando 1984) during the 28-day treatment period, the assigned study medication will be discontinued, all exit visit procedures (Visit 6) will be completed and subject will be followed in an observational period starting as OBS Visit 1 (Day 1) in which subjects will undergo VFQ-25, BCVA testing, CS testing and cornea verticillata grading. All subjects with cornea verticillata will return for monthly surveillance visits (OBS Visit 2, 3 and 4) where they will undergo BCVA testing and cornea verticillata grading for 3 months. If cornea verticillata persists at the 3-month time point

(OBS Visit 4), subjects will return every 2 months for BCVA testing and cornea verticillata grading until resolution or stabilization. Resolution is defined as grading of zero of the cornea verticillata grading and stabilization is defined as no worsening of the cornea verticillata grading for a minimum of one year from the commencement of dosing. Once resolution or stabilization is confirmed in both eyes, the subject will undergo VFQ-25, BCVA testing, CS testing and exit the study.

3.2 Rationale for Study Design and Control Group

In order to further evaluate the hypotensive efficacy of netarsudil ophthalmic solution relative to its placebo in subjects with OAG or OHT and to generate additional safety data for netarsudil in Japanese population, a double-masked, parallel group, 4-arm active- and placebo-controlled study design was selected.

As the intended route of administration for netarsudil ophthalmic solution is topical ocular, this is the route to be used in this study. The dosage regimen selected for this study is based on a previously completed Phase 2 study (AR-13324-CS201) and 4 completed Phase 3 studies (AR-13324-CS301, AR-13324-CS302, AR-13324-CS303, and AR-13324-CS304).

A Phase 1 study (AR-13324-CS104) evaluating the ocular and systemic safety of 2 concentrations of netarsudil (0.02% and 0.04%) ophthalmic solution compared to placebo over a 7-day period was conducted in healthy volunteers of Japanese ethnicity within the second generation in the United States. However, efficacy results with netarsudil ophthalmic solution to date have been generated in a mostly non-Japanese population. In order to ensure that similar results are observed in Japanese subjects, this study is being conducted in subjects in Japan.

The design of the observational period for subjects who develop cornea verticillata during the study is based on an observational study conducted in the United States in a non-Japanese population (AR-13324-OBS01). Per discussion at PMDA meeting, long term follow-up is necessary in order to understand the impact on visual function and resolution of cornea verticillata in Japanese population.

3.3 Expected Duration of Subject Participation

Each subject is planned to undergo a minimum washout period of their current ocular hypotensive medications (if needed), followed by approximately 28 days of treatment. Treatment duration with the investigational product (IP) for this study will start on the evening of Visit 3 (Qualification Visit #2; Day 1) and end on the evening before Visit 6 (Week 4/Day 28).

If a subject develops cornea verticillata during the 28-day treatment period, the duration of the study will continue until resolution or stabilization of the cornea verticillata. This observational period has no set duration since resolution of cornea verticillata varies from subject to subject. The Sponsor's expectation is that subjects will participate until resolution of the cornea verticillata.

4. STUDY POPULATION SELECTION

4.1 Study Population

A total of approximately 208 Japanese subjects will be enrolled in this study at approximately 30 investigational sites in Japan comprising a total of 52 subjects per treatment arm for each of the 4 treatment arms. Subjects will be at least 20 years of age with diagnosed OAG or OHT, each of whom meets all inclusion criteria and none of the exclusion criteria.

Planned enrollment numbers are higher (208 total, 52 subjects per arm) than statistically required for demonstrating efficacy (approximately 49 intent-to-treat [ITT] subjects per arm for 90% power) to account for the potential for subjects who do not complete the entire dosing period, or who have disqualifications. Over-enrollment (beyond 208 subjects) is to be undertaken only after communication between the investigational site and the Sponsor representative.

4.2 Inclusion Criteria

Subjects have to meet all of the following criteria at screening and qualification visits to enter into the study:

1. Must be of 20 years of age or older
2. Diagnosis of open-angle glaucoma (OAG) or ocular hypertension (OHT) in both eyes (OAG in one eye and OHT in the fellow eye is acceptable)
3. Medicated intraocular pressure (IOP) ≥ 14 mmHg in at least one eye and < 30 mmHg in both eyes at screening visit (this also applies to treatment naive subjects)
4. For OAG eyes, unmedicated (post washout) IOP ≥ 15 mmHg and < 35 mmHg in the study eye at 2 qualification visits (09:00 hours), 2-7 days apart. At second qualification visit IOP ≥ 15 mmHg and < 35 mmHg at 11:00 and 16:00 hour (in the same eye).
Note: For purposes of determining eligibility of subjects to be enrolled, any non-integral mean IOP number should not be rounded
5. For OHT eyes, unmedicated (post washout) IOP ≥ 22 mmHg and < 35 mmHg in the study eye at 2 qualification visits (09:00 hours), 2-7 days apart. At second qualification visit IOP ≥ 22 mmHg and < 35 mmHg at 11:00 and 16:00 hours (in the same eye)
Note: For purposes of determining eligibility of subjects to be enrolled, any non-integral mean IOP number should not be rounded
6. BCVA 0.1 or better in decimal unit using Landolt-C chart or its equivalent (+ 1.0 logMAR or better by Early Treatment of Diabetic Retinopathy Study [ETDRS] or 20/200 or better by Snellen chart)

7. Be able and willing to give signed informed consent and follow study instructions

4.3 Exclusion Criteria

Subjects meeting any of the following criteria during screening or qualification evaluations (e.g., at the time of randomization) will be excluded from entry into the study:

Ophthalmic:

1. Clinically significant ocular disease (e.g., corneal edema, uveitis, or severe keratoconjunctivitis sicca) which might interfere with interpretation of the study efficacy endpoints or with safety assessments, including subjects with glaucomatous damage so severe that washout of ocular hypotensive medications for up to 8 weeks is not judged safe as it would put the subject at risk for further vision loss
2. Pseudoexfoliation or pigment dispersion component glaucoma, history of angle closure glaucoma, or narrow angles (i.e., Shaffer Grade 2 or less). Note: Previous laser peripheral iridotomy is NOT acceptable
3. Ocular hyperemia score of moderate (+ 2) or severe (+3) at Qualification Visit #2
4. Previous glaucoma intraocular surgery, including selective laser trabeculoplasty (SLT) or argon laser trabeculoplasty (ALT) in the study eye
5. Refractive surgery in either eye (e.g., radial keratotomy, photorefractive keratectomy [PRK], laser-assisted in situ keratomileusis [LASIK], corneal cross-linking)
6. Ocular trauma within the 6 months prior to screening, or ocular surgery or non-refractive laser treatment within the 3 months prior to screening
7. Recent or current evidence of ocular infection or inflammation in either eye. Current evidence of clinically significant blepharitis, conjunctivitis, keratitis, or a history of herpes simplex or zoster keratitis in either eye at screening
8. Any corneal disease or condition in the either eye that in the investigator opinion, may confound assessment of the cornea
9. Current evidence of corneal deposits or cornea verticillata in either eye
10. Use of ocular medication in either eye of any kind within 30 days of screening and throughout the study, with the exception of a) ocular hypotensive medications (which must be washed out according to the provided schedule), b) lid scrubs (which may be used prior to, but not after, screening), c) lubricating drops for dry eye (which may be used throughout the study), or d) non-steroid allergy drops (note: must not contain a vasoconstrictor) as prescribed by the Investigator
11. Mean central corneal thickness greater than 620 μm in either eye at screening

12. Any abnormality preventing reliable applanation tonometry of either eye (e.g., keratoconus)
13. Known hypersensitivity to benzalkonium chloride or excipients of netarsudil ophthalmic solution
14. Cannot demonstrate proper delivery of the eye drop, or, in the principal investigator or co-investigator's opinion, unable to deliver the eye drop consistently

Systemic:

15. Current use of systemic medications known to cause corneal deposits or cornea verticillata including nonsteroidal anti-inflammatory drugs (NSAIDs), amiodarone, chlorpromazine, hydroxychloroquine, tamoxifen and phenothiazines
16. Clinically significant abnormalities in laboratory tests at screening
17. Clinically significant systemic disease which might interfere with the study
18. Participation in any investigational study within 30 days prior to screening
19. Systemic medication that could have a substantial effect on IOP within 30 days prior to screening, or anticipated during the study, including any corticosteroid-containing drug regardless of route of administration
20. Women of childbearing potential who are pregnant, nursing, planning a pregnancy, or not using a medically acceptable form of birth control. Acceptable birth control includes: condoms plus intrauterine devices or condoms plus oral hormonal contraceptives, double barrier methods (e.g., condoms with spermicidal gel plus diaphragms). Birth control must be continued for at least 30 days after the last dose of the study drug. An adult woman is considered to be of childbearing potential unless she is 1 year post-menopausal or 3 months post-surgical sterilization. All females of childbearing potential must have a negative urine pregnancy test result at the screening examination and must not intend to become pregnant during the study

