5.6 Concomitant Therapy

As noted in Section 5.7.1, subjects using ocular hypotensive medications at screening are required to undergo a washout of their current ocular hypotensive medications. Intermittent use of over-the-counter (OTC) artificial tear lubricant products is acceptable, with a minimum of 10 minutes between OTC products and study medication.

Prohibited medications include concurrent therapy of:

- Any form of ocular hypotensive medications (prescription or OTC)
- Miotics
- Epinephrine-related compounds
- Carbonic anhydrase inhibitors
- α -adrenoceptor agonists

- β -adrenoceptor antagonists
- Muscarinic agonists (e.g., pilocarpine)
- Ocular prostaglandin analogues
- Rho kinase inhibitors
- Any corticosteroid containing ocular or systemic drug regardless of route of administration
- Systemic medications known to cause corneal deposits or cornea verticillata including nonsteroidal anti-inflammatory drugs (NSAIDs), amiodarone, chlorpromazine, hydroxychloroquine, tamoxifen and phenothiazines

Systemic therapy with agents other than corticosteroids that could have an effect on IOP is to be consistent in dose, regimen and agent within the 30 days prior to screening and throughout the study is allowed. For example, a subject can be treated with a systemic β -adrenoceptor antagonist as long as the particular agent and its dose and regimen had been consistent for the 30 days prior to screening, and there is no reason to believe that alteration would be necessary at some point later during the study. Subjects should be cautioned to avoid use of alcohol or the use of any drugs such as cannabis or marijuana during the study visit days.

Contact lens wear during the study is acceptable. However, subjects must remove their contact lenses at least 30 minutes before instillation of study medication, and not place them in their eye(s) until 30 minutes after instillation. Subjects will be informed that benzalkonium chloride contained in this study drug as preservative agent has a risk to distain contact lenses.

Use of all medications should be documented on the appropriate case report form (CRF). Investigators are encouraged to contact the Sponsor/Sponsor representative for any questions regarding allowed medications. Judgment of continued study participation by the subject, and inclusion of this subject's subsequent visits in the safety and efficacy analysis will be made by the Sponsor.

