5.7 Restrictions

5.7.1 Prior Therapy/Washout Period

Subjects currently using ocular hypotensive medications must undergo a minimum washout period as specified in Table 1.

If washout is to be extended beyond 8 weeks (56 days) for logistical or other reasons, the Sponsor should be contacted.

Table 1 Ocular Hypotensive Medication Washout Period

Medication Class	Minimum Washout Period
Rho kinase inhibitor	6 weeks
Prostaglandins	4 weeks
β -adrenoceptor antagonists	4 weeks
Adrenergic agonists (including α -agonists such as brimonidine and apraclonidine)	2 weeks
Muscarinic agonists (e.g., pilocarpine), carbonic anhydrase inhibitors (topical or oral)	5 days

[Hughes 2005](#)

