7.1.2 Washout

As noted in Section 5.7.1, a washout period is required for individuals currently using ocular hypotensive medications and who meet the other qualifications for enrollment.

7.2 Visit 2 (Qualification Visit #1, for IOP and safety measurements at 09:00 hours)

After the washout (if needed), individuals will return to the Investigator's office in the early morning. The subject will be questioned regarding any changes in their health or concomitant medication use. Any change in the individual's Visit 1 health status should be recorded on the Medical History page of the CRF (e.g., the subject has been diagnosed with cancer).

Inclusion/exclusion criteria will be reviewed again for the qualified individual. Results of the clinical laboratory tests from Visit 1 need to be available and reviewed by the Investigator.

For subjects who were unable or unwilling to have blood drawn and urine collected for the clinical labs at Visit 1, the blood and urine sample may be drawn at Visit 2 (Qualification Visit #1) so long as the results of the clinical labs are available for that subject prior to Visit 3 (Qualification Visit #2).

The following procedures will be performed:

- Heart rate and blood pressure

- Symptomatology: Individuals will be asked “How are you feeling?”
- BCVA
- A non-dilated eye examination will be performed, including IOP measurements and biomicroscopy. IOP must be measured between 09:00 and 09:30 hours.

For further evaluation of OAG eyes in the study, at this time, unmedicated (post washout) IOP must be ≥ 15 mmHg and < 35 mmHg in both eyes. For further evaluation of OHT eyes in the study, at this time, unmedicated (post washout) IOP must be ≥ 22 mmHg and < 35 mmHg in both eyes. **This is the first of the four qualifying IOPs for randomization.**

Individuals who do NOT meet the IOP requirements above may return for up to 2 additional qualification visits within 1 week of failing this qualification visit. Individuals returning for an unscheduled visit within 1 week to re-attempt IOP qualification are required to only re-measure IOP in both eyes.

Individuals who screen fail due to IOP being ≥ 35 mmHg in either eye (exclusion criterion) MAY NOT return for additional qualification visits.

Qualified individuals will be scheduled to return 2-7 days later for the second qualification visit.

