7.3 Treatment Period

7.3.1 Visit 3.0 (Qualification Visit #2, Day 1, for IOP and safety measurements at 09:00 hours)

Within 2 to 7 days after Visit 2, individuals will return to the Investigator’s office for the next 09:00 hour IOP measurement.

The results of the clinical laboratory tests from Visit 1 or Visit 2 (if not performed at Visit 1) need to be available and reviewed by the Investigator. In order for the individual to be enrolled, the tests CANNOT be indicative of any clinically significant disease in the opinion of the Investigator.

The subject will be questioned regarding any changes in their health or concomitant medication use. Any change in the individual’s health status should be recorded on the Medical History page of the CRF (e.g., the subject has been diagnosed with cancer).

Inclusion/exclusion criteria will be reviewed again for the qualified individual.

The following procedures will be performed:

- Heart rate and blood pressure
- Symptomatology: Individuals will be asked “How are you feeling?”

- VFQ-25
- BCVA
- CS testing
- A non-dilated eye examination will be performed, including IOP measurements and biomicroscopy. IOP must be measured between 09:00 and 09:30 hours.

For further evaluation of OAG eyes in the study, at this time, unmedicated (post washout) IOP must be ≥ 15 mmHg and < 35 mmHg in both eyes. For further evaluation of OHT eyes in the study, at this time, unmedicated (post washout) IOP must be ≥ 22 mmHg and < 35 mmHg in both eyes. **This is the second of the four qualifying IOPs for randomization.**

Qualified individuals will continue with the measurements of IOP at 11:00 hours and 16:00 hours.

Individuals who do NOT meet the IOP requirements above may return for up to 2 additional qualification visits within 1 week of failing this qualification visit. Individuals returning at an unscheduled visit within 1 week are required to only re-measure IOP in both eyes.

Upon return for an unscheduled qualification visit, such individuals' IOP measurements would need to qualify at 09:00, 11:00, and 16:00 hours. Individuals who fail due to IOP being ≥ 35 mmHg in either eye (exclusion criterion) MAY NOT return for additional qualification visits.

Individuals are allowed to leave the Investigator's office between assessments and eat and drink with no restrictions. However, individuals are not to consume alcohol or engage in strenuous exercise.

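### Exclusion 1 asks whether up to 8 weeks of washout is safe but leaves out the qualification interval and 28 days of possible placebo, which take some washed-out subjects past 8 weeks

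*Protocol*

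**What the plan says.** Exclusion 1, in the synopsis and in Section 4.3, covers clinically significant ocular disease. Within it are subjects with "glaucomatous damage so severe that washout of ocular hypotensive medications for up to 8 weeks is not judged safe", because of the risk of further vision loss.

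Section 5.7.1 sets the washout: "Subjects currently using ocular hypotensive medications must undergo a minimum washout period as specified in Table 1". Table 1 gives minimums of 6 weeks (Rho kinase inhibitors), 4 weeks (prostaglandins; beta-antagonists), 2 weeks (adrenergic agonists) and 5 days (muscarinic agonists; carbonic anhydrase inhibitors). It adds: "If washout is to be extended beyond 8 weeks (56 days) for logistical or other reasons, the Sponsor should be contacted". Section 3.1 places the washout before Qualification Visit #1.

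The calendar then continues. Section 7.2 says: "Qualified individuals will be scheduled to return 2-7 days later for the second qualification visit". Section 3.3 describes washout "followed by approximately 28 days of treatment". Section 5.6 prohibits other ocular hypotensives during the study. Section 5.4 randomizes 1:1:1:1, and the placebo in Section 5.1.2 is vehicle without netarsudil. Subjects who miss the IOP requirement "may return for up to 2 additional qualification visits within 1 week of failing this qualification visit" (Section 7.3.1, with similar text in 7.2, 7.3.2 and 7.3.3).

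**The concern.** Exclusion 1 is the one entry criterion that addresses the severity of glaucomatous damage directly. It asks about the washout phase only. For a subject randomized to placebo, time without IOP-lowering treatment does not stop when washout ends; it runs on through qualification and the masked period. No section asks the investigator to judge that combined period.

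An investigator who follows the wording exactly could accept a subject for whom 8 weeks off therapy is tolerable but a longer period is not, and that subject has a one-in-four chance of placebo. What is at stake is subject protection at entry. The efficacy analysis is not affected.

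**Working it through.** **Inputs (Protocol).** Washout *W* to Qualification Visit #1: Table 1 minimums, or 56 days (Section 5.7.1). Gap *G* from Qualification Visit #1 to Day 1: 2 to 7 days (Section 7.2). Masked period *T* from Day 1 to Day 29: 28 days (synopsis; Section 3.3). Visit 6 window: ±3 days (Section 7.3.3).

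**The plan's own figure.** 8 × 7 = 56 days, the same as the 56 days in Section 5.7.1. The 8 weeks in exclusion 1 is therefore reproduced as the washout phase alone.

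**Time off therapy on placebo to nominal Day 29** = *W* + *G* + *T*, without re-qualification:

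| Prior therapy | W (days) | W + G + T | Total (days) | Weeks | Against 56 days |
|---|---|---|---|---|---|
| Muscarinic agonist or carbonic anhydrase inhibitor | 5 | 5 + (2 to 7) + 28 | 35–40 | 5.0–5.7 | under |
| Adrenergic agonist | 14 | 14 + (2 to 7) + 28 | 44–49 | 6.3–7.0 | under |
| Prostaglandin or beta-antagonist | 28 | 28 + (2 to 7) + 28 | 58–63 | 8.3–9.0 | 2–7 over |
| Rho kinase inhibitor | 42 | 42 + (2 to 7) + 28 | 72–77 | 10.3–11.0 | 16–21 over |
| Any class, washout run to 56 days | 56 | 56 + (2 to 7) + 28 | 86–91 | 12.3–13.0 | 30–35 over |

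**Break-even.** The total stays within 56 days only if *W* ≤ 56 − 28 − *G*, that is 26 days with a 2-day gap and 21 days with a 7-day gap. The 4-week and 6-week minimums both exceed this. The shorter classes exceed it only if their washout is extended or re-qualification adds time.

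**Visit 6 window.** The shortest 4-week case with Visit 6 on Day 26 is 28 + 2 + 25 = 55 days, just under 8 weeks. A Visit 6 three days late takes the 91-day case to 94 days (13.4 weeks).

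**Re-qualification.** Retries can lengthen the period, but the texts do not fit together cleanly. A 7-day gap followed by a Visit 3 retry a week later would put the qualifying visits 7 + 7 = 14 days apart, while inclusions 4 and 5 require 2 to 7 days. Section 7.3.3 also counts its retry week from failure of the first qualification visit, whereas Sections 7.3.1 and 7.3.2 count from failure of the current one. No firm maximum can be derived.

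**The case against.** The strongest reply is that nothing stated is wrong. Exclusion 1 says washout, washout ends at Qualification Visit #1, and 8 weeks matches Section 5.7.1. That stands: a reader might infer that the 8-week figure is an error or contradicts Section 5.7.1, and the documents do not support this. The gap is what the criterion leaves out.

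A second reply is that many subjects are untouched. This also stands. A reader might infer that every washed-out placebo subject goes 8 to 13 weeks without treatment. The table shows otherwise: two Table 1 classes stay under 8 weeks at minimum washout, the 4-week classes exceed it by only 2 to 7 days, and the 13-week end needs a washout at least two weeks longer than any Table 1 minimum.

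A third reply points to other safeguards. Screening IOP must be below 30 mmHg and post-washout IOP below 35 mmHg, and a subject at 35 mmHg or more may not retry. Criteria are reviewed again up to randomization, IOP is measured at Weeks 1 and 2, and Section 6.20.2 allows withdrawal for lack of efficacy or on the investigator's decision. So it would be wrong to say that subjects are unprotected or cannot leave. These measures do not close the gap, however. The IOP limits do not address severity of damage. The repeated review asks the same washout question when washout is already over. Withdrawal acts only after entry.

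**Conclusion.** The point holds in a limited form. As written, exclusion 1 omits the 30 to 35 days (2 to 7 plus 28) that follow washout for a placebo subject. On the nominal calendar, time off therapy exceeds the 8 weeks named by 2–7 days for the 4-week classes, 16–21 days for Rho kinase inhibitor users, and 30–35 days if washout runs to 56 days. The last two are the material cases.

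This assumes Day 29 on schedule, no re-qualification, and a placebo subject who completes. A reader might add every retry and quote an outer limit of about 15 weeks, but the retry wording and the 2-to-7-day requirement are not clearly compatible, so that figure is not supported. The documents give no distribution of prior medication, so neither the share of the 52 planned placebo subjects affected nor the number for whom the difference would matter can be computed.

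The protocol text reviewed is Amendment 1. The SAP introduction cites an Amendment 2, whose wording was not available.

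**What to change.** Reconcile exclusion 1 (synopsis and Section 4.3), Section 5.7.1 and the visit calendar, so that the period the investigator is asked to judge matches the whole period off IOP-lowering therapy that the protocol can impose: washout, qualification, any re-qualification, and possible placebo to Week 4. Settle at the same time how the retry text in Sections 7.2 and 7.3.1 to 7.3.3 fits with the interval in inclusions 4 and 5, since the length of the period depends on it.

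How long a period is acceptable, and whether the sponsor-contact rule in Section 5.7.1 should change, are for the sponsor and investigators. The cost is amendment wording, and possibly a few subjects with more advanced damage excluded at screening. Sample size and analysis are unchanged.
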